10.1 General Considerations

The Clinical Investigation will be conducted under conditions of respect for the fundamental rights of the person and the ethical postulates that affect biomedical research with human beings, following the international recommendations included in the Declaration of Helsinki, and their subsequent revisions. Likewise, the national recommendations will be followed in accordance with the guidelines of the Spanish Agency of Medicines and Medical Devices.

During the conduct of this study, the researchers will strictly comply with the provisions of this protocol, fully completing the Data Collection Notebook.

10.2 Informed Consent

In accordance with the criteria of good clinical practice, the subjects will be duly informed of all the details concerning their participation in the study and will freely give their consent in writing.

10.3 About the Participating Staff

The researchers will follow the Good Clinical Practice guidelines. All information collected during the study must be recorded directly in the CRF. Any correction made in the CRF must be accompanied by the date and initials of the person who makes them.

15.2.1. Responsibilities

1. Investigator

The researcher must comply with following obligations:

- Commit to carry out the study in accordance with what is established in its protocol, ensuring that your participation in this study does not alter your clinical responsibilities or the normal functioning of the Service to which you belong.
- Inform those responsible for the management of the center to which they belong to their participation in the study.
- Inform research subjects and obtain their consent.
- Collect, record and notify the data correctly responding to its update and quality before the appropriate audits.
- You must answer any questions about the objectives, basic methodology and meaning of the results of the study before the scientific and professional community.

- Facilitate the inspections of the health authorities, which will keep the study documentation a minimum of 5 years after the presentation of the final report.
- It will be responsible for the information recorded in the CRD being accurate, truthful and obtained in the manner indicated in the protocol.
- The investigator is the only person who can and should know the origin of the data collected and associate them with the patient, being responsible for not showing in the CRD extra (unclaimed) information that can identify the patient (name, DNI / NIF, NASS, CIP, postal address, telephone ...).
- Especially, the researcher must ensure at all times the best possible care of the patient, always putting the well-being and safety of his patients.

2. Coordinating Investigator:

- The coordinating researcher must fulfill all the obligations as a researcher of the study and also must sign the protocol and any modification thereof together with the promoter, will be responsible together with the promoter in the preparation of the monitoring and final reports, will contribute to disseminate the results of the study in collaboration with the promoter.
- Send the protocol to the CEIm.

3. Sponsor:

- Will be responsible for ensuring compliance with the relevant legal regulations.
- Sign the protocol and any modification of it with the coordinating investigator.
- Present the study protocol and the follow-up and final reports, within the established deadlines and communicate, where appropriate, the interruption and the reasons for it.
- Provide a copy of the protocol and the documents that accredit the follow-up of the established procedures to those responsible for the entities providing health care services where the study will be carried out.

10.4 Security Devices and Confidentiality

The information obtained in the present study is confidential, with patients accepting, in writing, that researchers and Health Authorities have access to their medical records to verify the data or procedures of the study, without violating the

confidentiality of the data compliance with current legislation. In each participating centre, the clinical data will be identified by an alphanumeric code, which does not allow to identify the personal data of the patients, such as name, initials, address or other personal characteristic. Likewise, the confidentiality of the identity of the patients would be respected if the data obtained in this study were published.

The data of the subjects included in the study will be treated in accordance with Regulation (EU) 2016/679 of the European Parliament and of the Council of April 27 2016 and according to the Spanish Law, The Organic Law 3/2018, of December 5, Protection of Personal Data and Guarantee of Digital Rights regarding the protection of individuals with regard to treatment of personal data and the free circulation of these data, and in the other applicable legislation in force regarding the protection of personal data.

11. - ECONOMICAL ASPECTS

11.1 Insurance Policy

According with current clinical trial legislation, this clinical trial does not require an insurance policy since the devices under study are used under the authorized conditions of use and the study does not imply an increase in the risk to the patient.

12. - PUBLICATIONS RIGHTS

Principal Investigator shall have the right to publish the results of the Study in any abstract, paper, presentation or manuscripts (not limited enumeration).

Principal Investigator shall give BOSTON SCIENTIFIC a reasonable period of 30 (thirty days) to review and comment upon an intended publication of Principal Investigator regarding the results of the Study prior to publication, to determine if any Intellectual Property Rights and/or Confidential Information should be removed. BOSTON SCIENTIFIC shall respond promptly in writing to Principal Investigator with any comments or objections, setting forth such information in reasonably sufficient detail.

Principal Investigator shall consider BOSTON'S SCIENTIFIC comments and/or objections in good faith and shall cause any and all appropriate changes to be made prior to further distribution and publication.

13. - STATISTIC ANALYSIS

A descriptive analysis of the categorical variables was performed using absolute and determined frequencies; and in the numerical variables, through the mean and

standard or median deviation and 25th and 75th percentiles, according to compliance with the assumption of normality.

The analysis of the main variable, pain difference between baseline measurement and 6 months after treatment in the radiofrequency group plus steroids vs steroids, will be carried out using a contrast of means with the t-Student or U Mann-Whitney test in case of not being able to fulfill the corresponding assumptions.

The size of the effect is estimated with Cohen's letter, interpreting a Cohen's letter <0.01 as "very small", between 0.01 to 0.2 as a "small" effect, around 0.5 an "average" effect ", from 0.8 to infinity, a" large "effect, according to the categorization of Cohen and Sawilowsky (Cohen, Jacob (1988). Statistical analysis of power for behavioral sciences. Routledge; Sawilowsky, S (2009). "New effect size rules of thumb". Journal of Modern Applied Statistical Methods. 8 (2): 467–474.).

If the imbalance is observed between the two groups, linear regression will be executed to adjust for variables that are observed unbalanced between them.

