7.3 Sample Size and justification

Pain reduction at least thirty millimeters between the baseline visit and the 6 months visit in patients assigned to the experimental group evaluated by the Visual Analogue Scale (VAS). Pain reduction of twenty millimeters less in the experimental group than in the control group since the baseline visit and the 6 months visit evaluated by the Visual Analogue Scale (VAS).

To achieve a power of 90.00% to detect differences in the contrast of the null hypothesis $H_0: \mu_1 = \mu_2$ through a bilateral T-Student Test for two independent samples, taking into account that the level of significance is 5%, and assuming that the mean of the difference in VAS of the 6-month radiofrequency plus steroid group is 40 mm, the average of the control group is 60 mm and the standard deviation of both groups is 30 mm, with an estimate of losses of the 20%, it will be necessary to include 62 patients per group, total of 124 patients.

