7.10 Definition of Population for Analyses

We define 3 different subject populations for analysis:

1. Intent-to-Treat (ITT)

- All subjects who receive any treatment of the groups (Experimental or Control)

2. Per Protocol (PP)

- All subjects who receive treatment of the study and complete the Primary Effectiveness Assessment (Primary Endpoint defined above).

3. ITT-Baseline (ITT-B)

- All subjects who complete baseline assessment. In order to capture AEs that occur prior to the 6 months follow-up visit.

8. – SAFETY ASPECTS

The definitions presented in this section allow for a clear understanding of adverse event data collection and reporting requirements.

Medical Device

Any instrument, apparatus, implement, machine, appliance, implant, software, material or other similar or related article.

Intended by the manufacturer to be used, alone or in combination, for human beings for one or more of the specific purpose (s) of:

- Diagnosis, prevention, monitoring, treatments or alleviation of disease,
- Diagnosis, monitoring, treatment, alleviation of, or compensation for, an injury,
- Investigation, replacement, modification, or support of the anatomy or of a physiological process,
- Supporting or sustaining life,
- Control of conception,
- Disinfection of medical devices and

Which does not achieve its primary intended action in or on the human body by pharmacological, immunological or metabolic means, but which may be assisted in its intended function by such means. The term 'medical device' is usually defined by national regulations.

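### Section 13 defaults to an unadjusted t-test on completers' VAS change, with two switches lacking operational criteria, no primary set and no missing-data rule; a pre-specified repeated-measures model is a cheap improvement

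*Combined protocol and SAP*

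**What the plan says.** Section 13 says the primary comparison "will be carried out using a contrast of means with the t-Student or U Mann-Whitney test in case of not being able to fulfill" the assumptions of the t-test. It then adds: "If the imbalance is observed between the two groups, linear regression will be executed to adjust for variables that are observed unbalanced between them". It gives no normality check, imbalance threshold or covariate list, and it does not rank the regression against the t-test.

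Section 7.3 sizes the trial "through a bilateral T-Student Test for two independent samples". It assumes 40 mm in the experimental arm, while "the average of the control group is 60 mm and the standard deviation of both groups is 30 mm", and it inflates the number "with an estimate of losses of the 20" per cent. It does not say whether 30 mm is the SD of the change or of the 6-month score.

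Section 7.10 defines three sets and names none as primary:
- ITT: "All subjects who receive any treatment of the groups (Experimental or Control").
- Per protocol: "All subjects who receive treatment of the study and complete the Primary Effectiveness Assessment".
- ITT-B: "All subjects who complete baseline assessment", with capture of adverse events as its stated purpose.

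Randomisation takes place at the Baseline visit (7.5.2), which may coincide with treatment. VAS is scheduled at Baseline and at months 1, 2, 4 and 6 (7.6, Table 1). Section 7.6 speaks of a mean leg-and-back score and also of leg and back changes. The form in Annex II, in the text available, shows only a back-pain line, which may be an extraction loss.

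**The concern.** An analyst following Section 13 must still decide when assumptions have failed, when groups count as unbalanced, which result is then primary, which patients are in, and what to do about a missing 6-month VAS. Investigators know the arm (7.2), so these choices are best fixed before outcomes are seen.

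A 6-month change cannot be computed without a 6-month VAS. With no imputation, patients lost earlier drop out of the primary test, although their scores at months 1, 2 and 4 may show why they left. At stake are some bias if loss follows pain, some precision, and a result that depends on late decisions.

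**Working it through.** **Inputs from the documents.** 7.3: difference 60 − 40 = 20 mm, SD 30 mm, two-sided 5%, 90% power, 20% loss, 62 per arm. 6.1: entry VAS of at least 5 points. **Assumed:** 5 points means 50 mm, so baseline lies in 50-100 mm (uniform SD 50/√12 = 14.4; SD at most 25). All correlations, extra covariates and dropout mechanisms are also assumed.

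**1. The plan's own number.** For 20/30 = 0.667 the two-sample t-test needs 48.26, so 49 per arm. 49/0.8 = 61.25, rounded up to 62. This matches 7.3. Power at 49 per arm is 90.4%.

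**2. Who is in the test.** Treated patients (ITT) who have a 6-month VAS are the same people as the per-protocol set. Either label gives about 62 × 0.8 = 49.6 per arm.

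**3. The two switches.** Simulation with 49 per arm and 9,000 null trials per threshold. Baseline-outcome correlation is 0.3, with six further covariates each correlated 0.15 with the residual. Shapiro p<0.05 triggers Mann-Whitney, and regression on any flagged covariate supersedes.
- Followed mechanically: type I error 4.7% (imbalance flagged at p<0.05) or 4.1% (p<0.2).
- Smallest p-value chosen: 6.4% or 6.8%. A free choice among t-test, Mann-Whitney and baseline-adjusted regression gives about 8.2% as a worst case.
- At a true 20 mm, the rule and the plain t-test disagree on significance in 2.4% or 4.5% of trials.

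**4. Baseline adjustment alone (ANCOVA).** Residual SD = s6·√(1 − r²), where s6 is the 6-month SD, sb the baseline SD and r their correlation. If 30 mm is the SD of change, s6 solves s6² + sb² − 2·r·s6·sb = 900. If 30 mm is the SD of the 6-month score, s6 = 30 and the change SD is √(900 + sb² − 60·r·sb). The residual SD never exceeds 30 mm on either reading, because the fitted slope does at least as well as a slope of 1 (the change score) or 0 (the raw score). Estimating the slope multiplies the variance by about 1 + 1/94. At SD 30 and 95 df, the floor is therefore about 90.1%.
- SD of change, sb 14.4, slope cost included: 90.9%, 90.2% and 90.4% at r 0.3, 0.4 and 0.5, against 90.4% for the t-test.
- SD of 6-month score, r 0.1-0.6: the t-test has 86.6-98.1% (sb 14.4) or 75.3-97.5% (sb 25). ANCOVA has 90.7-98.3% before the slope cost and 90.4-98.2% after it.

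**5. Using months 1, 2 and 4.** Random monotone loss over months 2, 4 and 6; post-baseline SDs 28/29/30/31 mm; correlation with baseline 0.3-0.4; month 4-6 correlation 0.5 to 0.85. The repeated-measures SE is 5.84 down to 5.62 mm. The t-test SE is 30·√(2/49.6) = 6.02 mm. Power is 92.4-94.1% against 90.8%.

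**6. Loss tied to the last recorded VAS.** 62 per arm, about 20% total loss, month 4-6 correlation 0.75. The slope is the rise in log-odds of loss per mm; at 0.04, a 20 mm higher VAS multiplies the odds by exp(0.8) = 2.2.

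| Scenario | 0.02 | 0.04 | 0.06 |
|---|---|---|---|
| Both arms, truth 20 mm: t-test | 19.6 | 18.2 | 17.2 |
| Both arms, truth 20 mm: repeated measures | 20.2 | 20.1 | 19.9 |
| Experimental arm only, truth 0: t-test bias (mm) | 1.7 | 3.1 | 4.0 |
| Experimental arm only: t-test type I error | 5.2-6.1% | 8.2-9.4% | 9.6-10.4% |

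The type I error ranges cover runs with slightly different assumed correlations. With loss alike in both arms and no true effect, the t-test rejects in 4.1-5.3%. With one-arm loss at 0.04-0.06, the repeated-measures estimate is about −0.1 mm and rejects about 5% (normal approximation). If loss depends on the unseen VAS (slope 0.04, truth 20 mm), the t-test gives 17.6 mm and repeated measures 18.7 mm. Neither method then removes the bias.

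**7. Delta analysis.** Adding d mm to imputed scores in the experimental arm moves the contrast by about 0.20·d. At d = 20 mm the shift is 4 mm, so 20 becomes 16 mm. With SE 5.70 mm, an observed 20 mm loses significance at d = (20 − 1.985 × 5.70)/0.20, or about 43 mm. A grid ending at 20 mm would not reach that point.

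**The case against.** Section 13 does name a condition for each switch, so a claim that there is no trigger would be wrong; only the operational criterion is missing. The unnamed primary set matters little for the planned test, since ITT and per protocol coincide without imputation. The gap between randomised and treated patients may be small when Baseline and Treatment fall on the same day. All of this stands.

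It is also fair that the rule followed as written does not inflate type I error, and that loss alike in both arms pulls the estimate towards the null. The only dropout pattern that raises type I error is assumed, and in its mildest case the rise is about one point or less. Sections 7.2 and 7.7 show that investigators know the arm and may request withdrawal; they do not show that loss will differ by arm.

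Finally, a pre-specified ANCOVA with a missing-data rule would close the specification gap too. That is true, but it would leave the month 1, 2 and 4 scores of lost patients unused unless the missing-data rule drew on them, and those scores are where the protection in step 6 comes from. A repeated-measures model also needs a degrees-of-freedom method and a fallback covariance, or it is under-specified in its turn.

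**Conclusion.** The point holds as a modest, conditional weakness that should be fixed. The primary analysis is not fully specified, is in effect restricted to completers, and ignores data already scheduled.

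Four stronger readings are tempting and not supported:
- **The switching rule inflates type I error.** It does so only if the most favourable result is picked, which the plan does not propose.
- **The trial is wrongly sized.** 62 per arm is reproduced exactly for the stated test.
- **Baseline adjustment brings a large gain in power.** Gains to 94-98% appear if baseline and 6-month variances are taken as equal. The entry threshold suggests a narrower baseline spread. If 30 mm is the SD of change, adjustment alone then adds almost nothing at mid-range correlation. The gain comes mainly from partial follow-up (SE about 5.6-5.8 against 6.0-6.1 mm).
- **Differential dropout is to be expected.** The documents make it possible, no more.

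The textual gaps rest on the documents alone. The sizes rest on assumed correlations, covariates and dropout mechanisms, and on normally distributed scores.

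**What to change.** 1. State which VAS (leg, back or their mean) is primary, and align 7.6 and the form.
2. Make the single primary analysis a mixed model for repeated measures on VAS at months 1, 2, 4 and 6, with arm, visit, arm-by-visit, baseline VAS, baseline-by-visit and unstructured covariance. State a small-sample degrees-of-freedom method and a fallback covariance. The primary contrast is the arm difference at 6 months with its 95% CI.
3. Analyse all randomised patients as randomised, name this as the primary set in 7.10, and report by arm those with no post-baseline VAS.
4. Delete the imbalance-triggered regression. Keep the t-test and Mann-Whitney as sensitivity analyses.
5. Add a missing-not-at-random analysis by multiple imputation, with a delta added to imputed scores in the experimental arm and increased until the conclusion changes.
6. Say in 7.3 whether 30 mm is the SD of change or of the 6-month score. N need not change: baseline-adjusted power at 49 per arm is about 90% or more on either reading.

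The cost is SAP wording and a little more programming, with no extra patients or visits. The price is reliance on missing at random, which item 5 tests.

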15.2 Annex II. Study Forms

NOTE: All forms will have the following header and footer so that they are perfectly identified

1.- Header:

"Epidural Pulse Radiofrequency for Treatment of Failed Back Syndrome: Prospective, Randomized, Single-Blind Study"

 EPIPUL	Patient ID Number:	Name:
	Date Of Visit (DD/MM/YYYY):	Sign:

2.- Footer:

Confidentiality: The data of the subjects included in the study will be treated in accordance with Regulation (EU) 2016/679 of the European Parliament and of the Council of April 27 2016 and according to the Spanish Law, The Organic Law 3/2018, of December 5, Protection of Personal Data and Guarantee of Digital Rights regarding the protection of individuals with regard to treatment of personal data and the free circulation of these data, and in the other applicable legislation in force regarding the protection of personal data.

15.2.1. Visual Analogue Scale (VAS)

VIAUSAL ANALOGUE SCALE (VAS) OF PAIN

Sponsor: Fundación Investigación HM Hospitales

Principal Investigator: [name] [name]

Protocol Code: EPIPUL

Form Version: 1.0 of 26th of July 2019

Pain assessment

Instructions: Place a vertical bar (|) in the place of the line that describes the average pain that have you felt in the last 7 days.

PAIN BACK

No Pain _____ The worst pain imaginable _____

Patient marked average (cm):

15.2.2. Oswestry Disability Index (ODI)

Oswestry Disability Index (ODI)

Sponsor: Fundación Investigación HM Hospitales

Principal Investigator: [name] [name]

Protocol Code: EPIPUL

Form Version: 1.0 of 26th of July 2019

Instructions: This questionnaire is designed to provide information on how back problems affect your ability to perform daily activities. Complete each section. In each one, check only the box that best suits your situation today.

Section 1: Pain Intensity

- I have no pain at the moment. [0 points]
- The pain is very mild at the moment. [1 point]
- The pain is moderate at the moment. [2 points]
- The pain is fairly severe at the moment. [3 points]
- The pain is very severe at the moment. [4 points]
- The pain is the worst imaginable at the moment. [5 points]

Section 2: Personal Care

- I can look after myself normally without causing extra pain. [0 points]
- I can look after myself normally but it is very painful. [1 point]
- It is painful to look after myself and I am slow and careful. [2 points]
- I need some help but manage most of my personal care. [3 points]
- I need help every day in most aspects of self care. [4 points]
- I do not get dressed, wash with difficulty and stay in bed. [5 points]

Section 3: Lifting

- I can lift heavy weights without extra pain. [0 points]
- I can lift heavy weights but it gives extra pain. [1 point]
- Pain prevents me from lifting heavy weights off the floor but I can manage if they are conveniently positioned, e.g. on a table. [2 points]

- Pain prevents me from lifting heavy weights but I can manage light to medium weights if they are conveniently positioned. [3 points]
- I can lift only very light weights. [4 points]
- I cannot lift or carry anything at all. [5 points]

Section 4: Walking

- Pain does not prevent me walking any distance. [0 points]
- Pain prevents me walking more than one mile. [1 point]
- Pain prevents me walking more than a quarter of a mile. [2 points]
- Pain prevents me walking more than 100 yards. [3 points]
- I can only walk using a stick or crutches. [4 points]
- I am in bed most of the time and have to crawl to the toilet. [5 points]

Section 5: Sitting

- I can sit in any chair as long as I like. [0 points]
- I can sit in my favourite chair as long as I like. [1 point]
- Pain prevents me from sitting for more than 1 hour. [2 points]
- Pain prevents me from sitting for more than half an hour. [3 points]
- Pain prevents me from sitting for more than 10 minutes. [4 points]
- Pain prevents me from sitting at all. [5 points]

Section 6: Standing

- I can stand as long as I want without extra pain. [0 points]
- I can stand as long as I want but it gives me extra pain. [1 point]
- Pain prevents me from standing for more than 1 hour. [2 points]
- Pain prevents me from standing for more than half an hour. [3 points]
- Pain prevents me from standing for more than 10 minutes. [4 points]
- Pain prevents me from standing at all. [5 points]

Section 7: Sleeping

- My sleep is never disturbed by pain. [0 points]
- My sleep is occasionally disturbed by pain. [1 point]
- Because of pain I have less than 6 hours sleep. [2 points]
- Because of pain I have less than 4 hours sleep. [3 points]
- Because of pain I have less than 2 hours sleep. [4 points]
- Pain prevents me from sleeping at all. [5 points]

Section 8: Sex Life (if applicable)

- My sex life is normal and causes no extra pain. [0 points]
- My sex life is normal but causes some extra pain. [1 point]
- My sex life is nearly normal but is very painful. [2 points]
- My sex life is severely restricted by pain. [3 points]
- My sex life is nearly absent because of pain. [4 points]
- Pain prevents any sex life at all. [5 points]

Section 9: Social Life

- My social life is normal and causes me no extra pain. [0 points]
- My social life is normal but increases the degree of pain. [1 point]
- Pain has no significant effect on my social life apart from limiting my more energetic interests, e.g. sport, etc. [2 points]
- Pain has restricted my social life and I do not go out as often. [3 points]
- Pain has restricted social life to my home. [4 points]
- I have no social life because of pain. [5 points]

Section 10: Traveling

- I can travel anywhere without pain. [0 points]
- I can travel anywhere but it gives extra pain. [1 point]
- Pain is bad but I manage journeys over two hours. [2 points]
- Pain restricts me to journeys of less than one hour. [3 points]

Pain restricts me to short necessary journeys under 30 minutes. [4 points]

Pain prevents me from travelling except to receive treatment. [5 points]

Douleur Neuropathique 4 questions (DN4)

Douleur Neuropathique 4 Questions (DN4)

Sponsor: Fundación Investigación HM Hospitales

Principal Investigator: [name] [name]

Protocol Code: EPIPUL

Form Version: 1.0 of 26th of July 2019

Instructions: Answer the four questions below with Yes or No for each item:

Question 1: dose your pain present one or more of the following characteristics?

1. Pain feels like burning YES / NO

2. Sensation of painful cold YES / NO

3. Pain feels like electric shocks YES / NO

Question 2: in the same area, is your pain associated to one or more symptoms?

4. Tingling YES / NO

5. Pins and needles YES / NO

6. Numbness YES / NO

7. Itching YES / NO

(Now your doctor will perform a physical examination)

Question 3: in is the pain located in an area where the exam unveils?

8. Hypoesthesia to touch? YES / NO

9. Hypoesthesia to pinprick? YES / NO

Question 4: is the pain provoked or increased by

10. Brushing? YES / NO

PATIENT SCORE:

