5.3 Secondary Endpoints

- 5.3.1. Change from Baseline in pain at 1, 2 and 4 months (assessed by Visual Analogue Scale, VAS).
- 5.3.2. Change from Baseline in disability at 1, 2 and 6 months (assessed by Oswestry Disability Index, ODI).
- 5.3.3. Change from Baseline in health survey at 1, 2, 4 and 6 months (assessed by Short Form Health Survey, SF-12).
- 5.3.4. Change from Baseline in neuropathic pain at 1, 2 and 6 months (assessed by Douleur Neuropathique 4 Questions, DN4).
- 5.3.5. Assessment of improvement of pain with experimental procedure at 1, 2, 4 and 6 months (assessed by Patient Impression of Improvement, PGI-I).
- 5.3.6. Incidence of unanticipated adverse device effects.
- 5.3.7. Change in opioid intake in 6 months.
- 5.3.8. Adverse events related to procedures (experimental group and control group).
- 5.3.9. Assessment of subject satisfaction with experimental procedure at 2 and 6 months.

6. - ELIGIBILITY CRITERIA

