7.2 Randomization Process

The clinical investigation will be single-blind. The assignment to the type of surgical treatment is carried out randomly and open for the investigators but not for

the patients. Randomization will be done with concealment of the randomization sequence and it takes place after informed consent has been signed.

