7.6 Evaluation Endpoints

▪ Primary endpoint

Visual Analogue Scale (VAS): The VAS measures the pain intensity reported by the subject. Subject scores the intensity of pain on a 10 mm line. The VAS in this study consists of a 10 mm line with one indicating “No Pain” and the other end indicating “Worst imaginable pain”. Upon completion by the subject VAS scores will be measured and converted to a numeric value (0.0 mm to 10.0 mm) by site staff personnel. VAS is the most widely used outcome measure in assessing pain due to its documented reliability and validity, ease in administration, and minimal training requirements for the administrator.

Subjects will complete a mean VAS score for leg and back pain: at Baseline, months 1, 2, 4, 6 and if applicable at the Unscheduled visit. The change in leg and back pain VAS scores, the percentage change in leg and back pain VAS scores, and the responder rate for leg and back pain will be calculated and summarized for each visit.

▪ Secondary Endpoints.

- Oswestry Disability Index (ODI): The ODI measures functional disability as reported by the subject. Subjects will complete ODI during the study visits: at Baseline, months 1, 2, 6 and if applicable at the Unscheduled visit. The changes in functional disability will be summarized as continuous variables.

- Short Form Health Survey (SF-12): The SF-12 measure health status reported by subject at: Baseline, months 1, 2, 4, 6 and if applicable at the Unscheduled visit. The changes in health status will be summarized as continuous variables.

- Douleur Neuropathique 4 Questions (DN4): The DN4 measures the neuropathic pain reported by the subject. Subjects will complete DN4 during the study visits: at Baseline, months 1, 2, 6 and if applicable at the Unscheduled visit. The changes in neuropathic pain will be summarized as continuous variables.

- Patient Impression of Improvement questionnaire (PGI-I): The PGI-I measure subjective improvement in pain. Subjects will complete PGI-I form during the study visits at: month 1, 2, 4, 6 and if applicable at the Unscheduled visit.

- Medication Usage: morphine equivalent units of opioid medications; other non-opioid pain medications. Assessed at: Baseline, months 1, 2, 4, 6 and if applicable at the Unscheduled visit.

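### Section 7.6 describes DN4 as subject-reported, but three of its ten items come from an examination by a doctor who may know the allocation; a sensitivity comparison of items 1 to 7 should be pre-specified.

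*Combined protocol and SAP*

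**What the plan says.** Section 5.3.4 lists DN4 as a secondary endpoint: "Change from Baseline in neuropathic pain at 1, 2 and 6 months". Section 7.6 describes the instrument with the words "The DN4 measures the neuropathic pain reported by the subject", has subjects complete it at each of those visits and at baseline, and plans to summarise the changes as continuous variables.

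The DN4 form in Annex II has ten yes/no items. Items 1 to 7 ask the patient about the character of the pain and associated symptoms. The form then states "Now your doctor will perform a physical examination" and continues with "8. Hypoesthesia to touch? YES / NO", "9. Hypoesthesia to pinprick? YES / NO" and, under a question on what provokes or increases the pain, "10. Brushing? YES / NO". It ends with a single line, "PATIENT SCORE". There is no line for an interview sub-score.

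On blinding, section 7.2 says that assignment is "carried out randomly and open for the investigators but not for" the patients. Section 7.4 adds only that the study is single-blind. Neither names a blinded or independent examiner. Section 13 gives no analysis specific to DN4 and does not separate patient-answered from examination items.

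**The concern.** The trial takes trouble to protect what patients report. In section 9.1 the control group has the electrode connected and the generator run at zero voltage so that patients cannot tell their arm. That protection covers items 1 to 7. It covers items 8 to 10 only in part, because how firmly a stimulus is applied, how the question is put and how a doubtful reply is recorded are all in the hands of an examiner who may know the arm.

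If the examiner's knowledge moved those items, a between-arm difference in DN4 change could arise partly from the examination. A report that followed section 7.6 would present it as subject-reported. With only the total available, nobody could tell whether the difference also appears in the items the patient answers alone.

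**Working it through.** **1. The two descriptions side by side.** Section 7.6: reported and completed by the subject. Annex II form: items 1 to 7 are put to the patient, and items 8, 9 and 10 follow a doctor's examination. The examination items number 3 of 10, so at most 3/10 = 30% of the score range is exposed to examiner influence. This is a ceiling on exposure and does not measure bias.

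**2. Baseline.** Section 7.5.2 lists randomization at the same visit as the baseline DN4. If patients are randomized before the form is completed, the baseline examination is also open to influence. Whether that would enlarge or offset a bias in the change score cannot be said from the documents.

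**3. Number of evaluable patients.** Section 7.3 gives no figure for DN4, so the primary VAS calculation is used to obtain n. Inputs: difference 60 − 40 = 20 mm, SD 30 mm, two-sided 5%, power 90%, losses 20%. A noncentral-t calculation gives 49 per group (power 90.4%). Then 49 / (1 − 0.20) = 61.25, rounded up to 62, which reproduces the plan's figure.

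**4. From altered answers to a shift in the score.** If a fraction f of all responses on the three items is changed in one arm and one direction, the mean total shifts by 3 × f:
- f = 0.05: 0.15 points
- f = 0.10: 0.30 points
- f = 0.20: 0.60 points

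Only answers that would have been yes can turn to no. If half would have been yes (an assumption), changing 10% to 20% of those gives 3 × 0.5 × 0.10 = 0.15 to 3 × 0.5 × 0.20 = 0.30 points.

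**5. Chance of p<0.05 with no true effect.** This assumes a two-sided two-sample t-test with n = 49 per arm (96 degrees of freedom). The noncentrality is shift / (SD × √(2/49)). With SD 2 the standard error is 2 × 0.202 = 0.404, so the noncentrality is 0.37, 0.74 or 1.49 for the three shifts. The documents give no SD for DN4 change, so a range is shown:

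| Shift (points) | SD 1.5 | SD 2.0 | SD 2.5 |
|---|---|---|---|
| 0.15 | 7.8% | 6.6% | 6.0% |
| 0.30 | 16.5% | 11.4% | 9.0% |
| 0.60 | 50.0% | 31.2% | 21.7% |

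The nominal rate is 5%. A small bias does little; a moderate one matters.

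**6. Effect of the fix on sample size.** None, since DN4 was not used for sizing. The power of a 7-item comparison cannot be computed, because the documents give neither an SD nor an expected effect for DN4.

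**The case against.** The strongest reply is that items 8 to 10 are not simply the doctor's judgement. Only the patient can feel whether brushing provokes pain, and reduced feeling to touch or pinprick also depends on what the patient says. This stands. A reader might infer that 30% of DN4 is unblinded; the form supports only that 30% of the range is open to some examiner influence.

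A reader might also take 11% to 31% as the false-positive rate of the plan. The documents do not support that. Those figures need 10% to 20% of all responses on the three items to change in one arm and one direction. If half the answers would have been yes, changing 10% to 20% of those gives 6.6% to 11.4% at SD 2. The plan also names a between-arm test only for the main VAS variable, so any rejection rate for DN4 is conditional on a test being used.

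Three further points have some force. The form says doctor, so a site could use one who is unaware of allocation; but nothing requires it. That DN4 will be analysed only as a total is inferred from the single score line and the wording of 7.6, and no sentence states it. Finally, Annex II prints the examination instruction openly, so the protocol does not hide it; section 7.6 still misdescribes the measure.

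It may be tempting to make items 1 to 7 the main DN4 comparison. Section 5.3.4 names DN4 itself, and nothing in the documents supports the sub-score as a replacement. It would also drop the examination signs from the comparison.

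**Conclusion.** The description in section 7.6 does not match the trial's own form. Up to 3 of 10 DN4 points are elicited by an examiner who may know the allocation, possibly at baseline as well as at follow-up, and no planned analysis shows whether a DN4 difference holds without those items.

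How large the resulting bias might be is unknown. The illustration (about 7%, 11% or 31% for shifts of 0.15, 0.3 or 0.6 points) rests on an assumed SD of 2, assumed shifts, 49 evaluable per arm and a t-test that the plan does not specify for DN4. It shows that the issue could matter, not that it will.

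DN4 is one of nine secondary endpoints. This is a cheap improvement and no threat to the trial's main conclusion.

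**What to change.** - In section 7.6, state that items 1 to 7 are answered by the patient and items 8 to 10 come from a physical examination by an examiner who is not blinded.
- Keep the change in the 10-item DN4 as the secondary endpoint of section 5.3.4.
- In Section 13, pre-specify a sensitivity comparison by arm of the change in items 1 to 7, reported beside the total at months 1, 2 and 6. Fix it before any analysis by arm, so that the sub-score cannot appear to have been chosen on its result.
- Enter the ten item answers in the CRF, not only the total.

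The cost is a few sentences, item-level data entry and one extra computed score. The downside is that this score has a narrower range (0 to 7) than the full instrument. It needs no extra visit, patient or assessor. It leaves the examination itself unblinded; having items 8 to 10 examined by someone unaware of allocation would address the cause directly, at the price of extra staffing.
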